8. INTERVENTION DISCONTINUATION

Study enrollment and/or interventions may be temporarily suspended or terminated if:

- Any study participant experiences death that the DSMB, PIs or IRB believes may be related to the study interventions.
- If a statistically or clinically significant number of SAEs or hospitalizations occur that the DSMB believes may be related to the treatment.
- New information from outside studies reveals that it would be unethical to continue enrolling participants in the study.
- The IRB decides that the study should be stopped.
- If statistical differences among the primary outcomes will be determined that require stopping. For example, if the differences among certain interventions make it unethical to continue or if the effect size is so small that it is implausible a positive outcome could occur.

A safety review by the DSMB, IRB, and/or NCCIH will be convened to determine if the study should continue per protocol, proceed with enhanced monitoring, be further investigated, be discontinued, or be modified and then proceed. The FDA and NCCIH retain the authority to suspend additional enrollment and study interventions and administration of study product for the entire study, as applicable.

This study will be stopped prior to its completion if:

- (1) the intervention is associated with adverse effects that call into question the safety of the intervention;
- (2) difficulty in study recruitment or retention will significantly impact the ability to evaluate the study endpoints;
- (3) any new information becomes available during the trial that necessitates stopping the trial; or
- (4) other situations occur that might warrant stopping the trial.

Individuals may be withdrawn from the study for any of the following:

- Adverse events; the clinical PI [name] will discuss AEs with the participant, and possibly with their personal physician, as needed, to determine whether the participant should be withdrawn from the study.
- If participant are deemed to be noncooperative (e.g. refuse to participate in follow-up calls or fail to complete diaries).
- If participants are lost to followup, i.e. more than 7 days without contact with study personnel during the follow-up period.
- Participant will not be withdrawn from the study solely for missed interventions or specimen collections, but may be withdrawn for non-cooperation or lost to follow-up.
- Serious adverse events related to the interventions, as determined by the PIs, participant or participant's physician.

9. STATISTICAL CONSIDERATIONS

9.1 General Design Issues

Primary Hypothesis: Antibiotics will result in a reduction in fecal SCFA. BB-12 supplementation will protect against antibiotic-induced SCFA (with acetate levels being used to represent the production of SCFA by gut microbiota) reduction and/or be associated with a more rapid return to baseline SCFA levels (acetate), compared to participants who receive a control yogurt without BB-12.

As reported by Hoverstad et al. (1986) and Clausen (1991), we hypothesize that antibiotic administration for 7 days will decrease mean fecal acetate levels for each participant, and that upon conclusion of antibiotic therapy fecal acetate levels will return toward baseline values for each participant.

We will compare the mean fecal acetate levels at days 7 and 30 versus the baseline values for participants receiving BB-12 or control yogurt. A significantly higher mean level of fecal acetate, calculated using one-way analysis of variance (Ganes-Howell *post hoc* test) in participants receiving BB-12 yogurt compared to the control yogurt during or after antibiotic administration, will be consistent with our hypothesis on the effect of BB-12, and will substantiate advancing the proposed study onto the next phase. As with the sample size calculation, we estimate a 42% decrease in acetate in the control/antibiotic treated group and no greater than a 15% decrease in the BB-12 treated group.

The following *biological signatures* will be assessed to determine if giving yogurt with BB-12 to humans results in a clinically meaningful change in these measures. We will move to the R33 phase if the R61 demonstrates the expected changes described for each signature, in the direction indicated:

- a. BB-12 ameliorated antibiotic-induced decreases in acetate. We expect a minimal effect size for comparison of the acetate levels in the placebo group to the BB-12-treated group to have a Cohen's $d \geq 0.6$. Effect size according to Cohen's d will be calculated at day 7 and day 30 with either day 7 or day 30 reaching Cohen's $d \geq 0.6$ constituting an achieved milestone in the R61 Phase that will justify movement to the R33 Phase. Based upon the literature, we expect a 42% decrease in acetate with antibiotics and no greater than 15% decrease in acetate with BB-12, which would yield a Cohen's $d > 0.6$.

Secondary Hypothesis: Antibiotics will result in a decrease in the overall number and diversity of bacterial species present in the fecal microbiota. BB-12 supplementation will protect against antibiotic-induced shifts in the microbiota and/or will be associated with a quicker return to a baseline microbiota composition, as compared to the control group. Microbiota composition will be assessed with 16S rDNA profiling and qPCR.

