9.2 Sample Size and Randomization

Sample size calculations were informed by data from Hoverstad et al.,(120, 121) which compared changes in the mean SCFA levels between baseline fecal samples and fecal samples collected after six days administration of various antibiotics or placebo in healthy volunteers. In these studies, a mean reduction in acetate levels occurred from 45 ± 16 umol/g at baseline to 24 ± 18 umol/g after antibiotic treatment (46% reduction in acetate). Reductions in acetate after antibiotic treatment ranged from 5% to 79% with ampicillin, a similar antibiotic to amoxicillin.(120, 121) We can infer similar decreases in acetate in our proposed study. Using a conservative estimate of a 42% decrease in acetate in the control/antibiotic treated group and no greater than a 15% decrease in the BB-12 treated group, and an allocation ratio of 2:1 (BB-12 to control volunteers); a total sample size of 60 participants is necessary to have 80% power to detect a significant difference in mean acetate levels as a measure of gut microbiota production of SCFA between a control and BB-12-treated group.

With a sample size of 40 subjects in the active arm and 20 subjects in the control arm and attrition rate of 5% at day six and 20% at day 30, we would have power of 82% to detect a moderate effect size of Cohen's $d = 0.63$ (assuming the intra-correlation correlation coefficient is 0.3). The α level of 0.05 will be used for the analysis. Since the effect size of previous study (reduction in acetate levels) is Cohen's $d = 1.23$, we should have ample power to detect the treatment effect. (The power calculation is based on the R software and packages simr, sjstats, and pwr).

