9.7 Data Analyses

To examine the primary hypothesis that BB-12 supplementation will protect against antibiotic-induced SCFA reduction, the mixed model will be used to analyze the treatment effect on the antibiotic-induced SCFA reduction. Statistical analyses will be performed using intent-to-treat analytic strategies. The mixed effect model will be used, which is compatible with unbalanced outcome measurements. The change of SCFA from baseline will be considered as the outcome variable of the mixed model. All time points will be included for the analysis. Covariates including age, sex, BMI and time (a continuous variable) will be adjusted when necessary. In addition, the time and treatment interaction term will be assessed by the likelihood ratio test. The random intercept will be used and the AR1 and/or compound symmetry covariance structure will be considered (and then the likelihood test can help to determine the more appropriate covariance structure). The final model selection will be performed based on information criteria such as Akaike information criterion (AIC) or Bayesian information criterion (BIC). Power: with a sample size of 40 subjects in the treatment arm and 20 subjects in the placebo arm and attrition rate of 5% at day six and 20% at day 30, we would have power of 82% to detect a moderate effect size of Cohen's $d = 0.63$ (assuming the intra-correlation correlation coefficient is 0.3). The α level of 0.05 will be used for the analysis. Since the effect size of previous study (reduction in acetate levels) is Cohen's $d = 1.23$, we should have ample power to detect the treatment effect. (The power calculation is based on the R software and packages simr, sjstats, and pwr).

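### The mixed model for the primary acetate hypothesis has no named deciding contrast, and section 9.1 adds an either-day test (day 7 or day 30) with no multiplicity control

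*Combined protocol and SAP*

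**What the plan says.** Sections 1.1, 3.1 and 9.5.1 place the primary outcome at day 7, with acetate as the marker. The hypothesis in 1.1 and 9.1 is wider: less reduction in SCFA, a faster return to baseline, or both.

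Two analyses are attached to that hypothesis.

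- **Section 9.1:** "We will compare the mean fecal acetate levels at days 7 and 30 versus the baseline values". The difference is "calculated using one-way analysis of variance" with a Games-Howell post hoc test. A significantly higher mean "in participants receiving BB-12 yogurt compared to the control yogurt during or after antibiotic administration, will be consistent with our hypothesis" and is also said to support moving to the next phase. A separate R33 milestone asks for Cohen's d of at least 0.6, "with either day 7 or day 30 reaching" it.
- **Section 9.7:** "the mixed model will be used to analyze the treatment effect on the antibiotic-induced SCFA reduction", with change from baseline as the outcome. "All time points will be included for the analysis", and "the time and treatment interaction term will be assessed by the likelihood ratio test". Section 9.3 also names the mixed model.

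On power, 9.2 and 9.7 both say "we would have power of 82% to detect a moderate effect size" of d = 0.63, at an alpha of 0.05 whose sidedness is not stated. The only multiplicity correction, in 9.8, is for the microbiota metrics.

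**The concern.** Section 9.7 gives the primary hypothesis a model but no deciding quantity. The treatment effect over all visits, the time-by-treatment interaction and the day-7 difference are different tests with different power, and the plan chooses none of them. Section 9.1 then gives a second route to a positive statement through either of two days, and nothing ranks the two sections.

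The R61 phase could therefore report support for its primary hypothesis from day 30 alone, with nothing significant at its own primary time point. The power of the primary claim also cannot be known until the test is named.

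**Working it through.** **Inputs.** 40:20 allocation, alpha 0.05, d = 0.63, intra-class correlation 0.3, attrition 5% at day six and 20% at day 30 (all from 9.2). Applying the 5% to day 7 gives 38:19 at day 7 and 32:16 at day 30. Two-sided testing is assumed, so one test has a 2.5% chance of falsely favouring BB-12.

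**Step 1: the plan's 82% power.**

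- *Day 7 alone, two-sample t-test, 38:19.* Noncentrality = 0.63 × √(38 × 19 / 57) = 0.63 × 3.559 = 2.24 on 55 df. Power = 59.6%.
- *Common effect over days 7 and 30, with attrition (normal theory).* A participant seen at both visits carries information 2/(1 + 0.3) = 1.538; one seen only at day 7 carries 1. BB-12: 32 × 1.538 + 6 = 55.2. Control: 16 × 1.538 + 3 = 27.6. SE = √(1/55.2 + 1/27.6) = 0.233. Power = Φ(0.63/0.233 − 1.96) = 77.1%.
- *Same, without attrition.* SE = √(1/61.5 + 1/30.8) = 0.221; power 81.4%. With 1:1 allocation and attrition it is 81.8%.
- *Four post-baseline visits (days 7, 14, 21, 30), assumed linear dropout.* With k visits the information is k/(1 + 0.3(k − 1)): 2.105, 1.875, 1.538 and 1 for k = 4, 3, 2 and 1. With 80%, 5.9%, 4.6% and 4.6% of each arm in those classes, the mean is 1.91 per randomized participant. SE = √(1/76.4 + 1/38.2) = 0.198; power about 89%.

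The 77.1% assumes SCFA is measured after baseline only on days 7 and 30, as Table 8 shows. The Précis (Interventions and Duration) and section 3 describe SCFA samples on days 14 and 21 as well.

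**Step 2: the 9.1 rule with a separate test on each day.** With two arms, Games-Howell on one day is a Welch test and adjusts nothing across days. P(false favourable on either day) = 0.025 + 0.025 − P(both).

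- *Correlation 0.3 between days.* Attrition lowers the correlation of the test statistics to 0.3 × √(32/38) = 0.275. P(both) = 0.0022; result 4.78% (simulated 4.8%).
- *Change from a shared baseline.* Correlation = (1 − 0.3)/(2 × (1 − 0.3)) = 0.5, or 0.459 with attrition. Result 4.59%.
- *Range.* 4.9% at correlation 0 to 4.1% at 0.8.
- *Day 30 only.* 4.78% − 2.5% = about 2.3% of null trials.

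**Step 3: other readings of the tests (simulated, correlation 0.3, with attrition).** The power column takes d = 0.63 on both days.

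| Reading | False favourable | Power |
|---|---|---|
| Day 7 alone | 2.5% | 59%-60% |
| Welch test per day, either day | 4.8% | 76% |
| Games-Howell on the three blinded labels of 6.6, per day, either day | 3.5% | not computed |
| Games-Howell over four arm-by-day cells | 1.0% | 49% |
| Games-Howell over six cells, with baseline | 0.5% | 36% |
| One pooled treatment test from 9.7, days 7 and 30 | 2.6% | 76% |

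**Step 4: the milestone.** Under no effect, observed d ≥ 0.6 in favour of BB-12 occurs on either day in about 4.5% of trials, against 1.9% for day 7 alone.

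**The case against.** The strongest reply is that the plan does have a primary analysis. Section 9.7 opens by tying the mixed model to the primary hypothesis, 9.3 repeats it, and the power statement uses mixed-model inputs. Section 9.1 is a general design section that speaks of consistency and advancement. This stands as far as it goes: a reader might infer that the plan names no primary analysis at all, and the documents do not support that. What is missing is the contrast, and a statement that 9.1 does not compete with it.

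Second, a reader might infer that the false-favourable rate is simply doubled. The documents do not support that either. A post hoc test built for several groups, the three blinded labels in 6.6 and the comparison with baseline all point to readings with lower rates, some below 2.5%. The 4.8% figure is the top of the two-sided range.

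Third, day 30 is prespecified and addresses the recovery half of the hypothesis. That explains its presence, but 9.5.1 does not list it as primary, and no error control covers the two routes.

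Fourth, 6.6 keeps the allocation hidden until the analyses are complete. This limits choosing a test because it favours BB-12. It does not tell a reader in advance which test counts.

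Finally, this is an exploratory pilot, and 9.6 says R33 would repeat the methods. That lowers the stakes. However, 9.8 calls only the secondary analysis exploratory, while the acetate analysis carries an alpha, a power claim and a significance-based statement about advancing.

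**Conclusion.** The concern holds as an unresolved specification of the primary test and should be corrected before analysis. Under the 9.1 rule the false-favourable rate is about 0.5% to 4.8%, depending on how Games-Howell is applied, against 2.5% for day 7 alone. The top of the range is 4.6% for change scores and 4.8% at correlation 0.3. It rests on separate tests per day, two-sided 0.05 and the plan's attrition. A single treatment test from 9.7 keeps the nominal level.

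The 82% power does not describe a test of the day-7 outcome, which has about 60% at d = 0.63. It may be tempting to call 82% an error, but the simulation model behind it is not described, and nearby assumptions give 81% to 82%. What can be said is that it needs more than day 7, and that two pooled visits with the plan's own attrition give about 77%.

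The main harm is an unclear R61 primary claim. Replication in R33 limits what follows from it.

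**What to change.** - **9.7:** state two-sided 0.05 and name the day-7 treatment contrast from the mixed model, with time categorical, as the single primary test, matching 9.5.1. Say which SCFA visits enter the model, and reconcile Table 8 with the Précis and section 3.
- **Day 30 (recovery):** make it secondary, or test it only after day 7 succeeds. If both days are meant to be primary, list both in 9.5.1 and apply Holm.
- **9.1:** delete the ANOVA/Games-Howell sentence, or label it supportive and say which groups it compares.
- **9.2 and 9.7:** restate the power for the named test.
- **Milestone:** the either-day d ≥ 0.6 rule can stay as a funding criterion, with a note that meeting it is not evidence for the day-7 primary outcome. Its false-Go rate (about 4.5% at correlation 0.3) can be given beside it.

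**Cost.** A paragraph each in 9.1 and 9.7, a revised power statement, and a line in 9.5.1 only if both days become primary. Sample size and the milestone do not change. The stated power becomes less favourable: about 60% at d = 0.63 for day 7 alone, with 80% reached only near d = 0.80. An effect confined to day 30 would no longer count as primary support. Holm across both days gives about 64% if d = 0.63 holds on both days, 48% if only on day 7 and 40% if only on day 30.

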9.2 Sample Size and Randomization

Sample size calculations were informed by data from Hoverstad et al.,(120, 121) which compared changes in the mean SCFA levels between baseline fecal samples and fecal samples collected after six days administration of various antibiotics or placebo in healthy volunteers. In these studies, a mean reduction in acetate levels occurred from 45 ± 16 umol/g at baseline to 24 ± 18 umol/g after antibiotic treatment (46% reduction in acetate). Reductions in acetate after antibiotic treatment ranged from 5% to 79% with ampicillin, a similar antibiotic to amoxicillin.(120, 121) We can infer similar decreases in acetate in our proposed study. Using a conservative estimate of a 42% decrease in acetate in the control/antibiotic treated group and no greater than a 15% decrease in the BB-12 treated group, and an allocation ratio of 2:1 (BB-12 to control volunteers); a total sample size of 60 participants is necessary to have 80% power to detect a significant difference in mean acetate levels as a measure of gut microbiota production of SCFA between a control and BB-12-treated group.

With a sample size of 40 subjects in the active arm and 20 subjects in the control arm and attrition rate of 5% at day six and 20% at day 30, we would have power of 82% to detect a moderate effect size of Cohen's $d = 0.63$ (assuming the intra-correlation correlation coefficient is 0.3). The α level of 0.05 will be used for the analysis. Since the effect size of previous study (reduction in acetate levels) is Cohen's $d = 1.23$, we should have ample power to detect the treatment effect. (The power calculation is based on the R software and packages simr, sjstats, and pwr).

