9.5 Outcomes

9.5.1 Primary Outcome

The primary outcome is a difference, measured at day 7, in antibiotic-induced changes in fecal SCFA (with a particular focus on acetate) in participants receiving BB-12-supplemented yogurt versus non-supplemented control yogurt.

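### The 82% power at d = 0.63 comes from pooling visits; the day-7 primary comparison has about 60%, and d = 1.23 is the antibiotic effect, not BB-12 versus control

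*Combined protocol and SAP*

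**What the plan says.** Section 9.5.1 fixes the time point: "The primary outcome is a difference, measured at day 7, in antibiotic-induced changes in fecal SCFA". Sections 1.1 and 3.1 also name acetate on day 7.

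Section 9.2 makes three statements about power:

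- For a 42% fall in acetate on control and at most 15% on BB-12, with 2:1 allocation, "a total sample size of 60 participants is necessary to have 80% power to detect a significant difference in mean acetate levels".
- With 40 and 20 participants, an "attrition rate of 5% at day six and 20% at day 30", and an intra-class correlation of 0.3, "we would have power of 82% to detect a moderate effect size of" Cohen's d = 0.63. Alpha is 0.05, and simr is among the packages named.
- "Since the effect size of previous study (reduction in acetate levels) is" d = 1.23, and from this the plan infers ample power.

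Section 9.7 repeats the second and third statements, ending "we should have ample power to detect the treatment effect". They follow a mixed model that uses all time points, of which the plan says "The change of SCFA from baseline will be considered as the outcome variable of the mixed model". Section 9.1 expects that "upon conclusion of antibiotic therapy fecal acetate levels will return toward baseline values".

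**The concern.** Comparing two arms at one visit needs neither an intra-class correlation nor attrition at day 30. Their presence shows that the 82% belongs to a repeated-measures effect averaged over visits, whereas the declared primary outcome is at day 7. Averaging also assumes that the arms differ equally at every visit, which is doubtful if acetate recovers once antibiotics stop.

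The 1.23 is described as the earlier study's reduction in acetate. A fall caused by antibiotics says nothing by itself about how well this trial can detect a difference between BB-12 and control yogurt.

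Section 9.1 treats a significantly higher acetate level with BB-12 as support for moving to the next phase. Anyone who reads a non-significant day-7 result as coming from a test with 82% or ample power will make too much of it.

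**Working it through.** **Inputs from the documents.** 40:20 allocation; alpha 0.05; d = 0.63; intra-class correlation 0.3; attrition 5% at day six and 20% at day 30; acetate 45 ± 16 µmol/g before and 24 ± 18 after antibiotic; planned falls of 42% and 15%.

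**Assumptions.** Two-sided test; the 5% loss applies at day 7, leaving 38:19; both planned falls start from 45.

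**1. Where the 82% comes from.** Under compound symmetry with ρ = 0.3, a participant seen at k visits contributes k/(1 + (k − 1)ρ): 1, 1.538, 1.875 and 2.105 for k = 1 to 4. With I the average contribution per randomised participant, λ = d·√(I × 40 × 20/60) and power is Φ(λ − 1.96).

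- Two visits, no attrition: I = 1.538, λ = 0.63 × √(13.33 × 1.538) = 2.853, power 81.4%. This is close to the plan's 82%, but it ignores the plan's own attrition.
- With retention falling linearly from 95% at day 7 to 80% at day 30:

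| Visits | I | λ | Power |
|---|---|---|---|
| 7, 30 | 0.80 × 1.538 + 0.15 × 1 = 1.381 | 2.703 | 77% |
| 7, 14, 30 | 1.706 | 3.005 | 85% |
| 7, 14, 21, 30 | 1.910 | 3.179 | 89% |

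Mixed-model simulations of a constant effect agree: 79% for two visits (600 runs) and 90% for four (400 runs). If instead the day-30 effect were half the day-7 effect (an assumption), power would be 56% for two visits and 70% for four with a linear fade.

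**2. Day 7 alone at d = 0.63.** Noncentral t with noncentrality d·√(n₁n₂/(n₁ + n₂)):

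- 40:20: 0.63 × √13.33 = 2.300, power 61.9%.
- 38:19: 0.63 × √12.67 = 2.242, power 59.6%.
- One-sided: 73.5% and 71.6%.
- Detectable d at 80% power, two-sided: 0.78 and 0.80.

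**3. The separate 80% claim.** The planned difference is 45 × (0.42 − 0.15) = 12.15 µmol/g. On acetate levels:

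| SD | d | 40:20 | 38:19 |
|---|---|---|---|
| 16 | 0.76 | 78% | 76% |
| 17.03 | 0.71 | 73% | 70% |
| 18 | 0.68 | 68% | 66% |

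The plan's 80% is approached only at SD 16 with no attrition (77.8% by t, 79.2% by normal approximation).

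On the change scale of 9.7, the SD is √(16² + 18² − 2r × 16 × 18), where r is the correlation between baseline and day 7. The plan does not give r.

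| r (assumed) | SD of change | d | Power, 38:19 |
|---|---|---|---|
| 0.3 | 20.18 | 0.60 | 56% |
| 0.5 | 17.09 | 0.71 | 70% |
| 0.7 | 13.30 | 0.91 | 89% |

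Reaching 80% needs r of at least 0.59 (40:20) or 0.61 (38:19).

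**4. What 1.23 is.** √((16² + 18²)/2) = 17.03 and (45 − 24)/17.03 = 1.233. This is the before/after antibiotic contrast and contains no BB-12 arm. The planned between-arm difference is 12.15/21 = 58% of it. A between-arm d of 1.23 would give about 99% power at 38:19, against 66% to 76% for the planned effect on levels.

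**The case against.** The strongest reply is that the 82% is attached to the analysis actually planned. Section 9.7 fits a mixed model to all time points, and the inputs are openly repeated-measures ones, so the figure is not bad arithmetic. Section 9.1 compares acetate at days 7 and 30, and the SCFA row of Table 8 appears to match that, which points to two post-baseline visits. That reading is plausible, but it gives 77% once the stated attrition is applied. The précis and the all-time-points wording in 9.7 also leave four visits possible. On any of these readings the figure describes a pooled effect, while the declared outcome is at day 7.

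A second reply is that 60% depends on d = 0.63, which is below the planned effect. That is true, and the figure should be read only at that d, which is the plan's own choice. At the planned effect, day-7 power on levels is 66% to 76% after attrition, still below 80%. Adjusting for baseline would help: at d = 0.63 and 38:19 it gives 64%, 72% and 87% for r = 0.3, 0.5 and 0.7. The plan states no correlation to rely on.

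Third, the fading-effect figures are an assumption. Section 9.1 also allows for a faster recovery with BB-12, which could sustain a difference after day 7. They show sensitivity and are not a forecast.

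Fourth, progression does not hang on the day-7 test alone. The significance criterion in 9.1 covers the period during or after antibiotics, the R33 milestone is an observed d of at least 0.6 at day 7 or day 30, and 9.6 defines a negative result by longitudinal acetate and microbiome changes together. This limits the consequence but does not make the power statements correct.

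**Conclusion.** The concern holds. At the plan's d = 0.63, the day-7 primary comparison has about 60% power (59.6% at 38:19, 61.9% at 40:20; two-sided 0.05, no baseline adjustment), so it would miss a real effect of that size about 40% of the time. The 82% is a pooled-visit figure that assumes an equal effect at each visit. With the stated attrition it becomes 77%, 85% or 89% for two, three or four visits. The exact simulation set-up cannot be confirmed because the power statement does not name the visits.

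The separate 80% claim is fragile rather than false: 66% to 76% on levels after attrition, and 56% to 89% on change for assumed correlations of 0.3 to 0.7. The ample-power inference from d = 1.23 does not follow, because that contrast does not involve BB-12.

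**What to change.** Keep N = 60 and revise 9.2 and 9.7 together:

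- State day-7 power as about 60% at d = 0.63 (two-sided 0.05, 5% attrition), with d of about 0.80 detectable at 80% power.
- Label the 82% as power for an effect pooled over repeated visits, name the visits, state that the effect is assumed equal at each, and recompute it with the stated attrition.
- For the 80% claim, give the SD, the scale (level or change), the baseline to day-7 correlation and the attrition. Report the range: 66% to 76% on levels, 56% to 89% on change for r from 0.3 to 0.7.
- Delete the d = 1.23 sentence, or label it as the antibiotic effect and quote the planned BB-12 versus control d instead (about 0.68 to 0.76 on levels).

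The cost is wording and one rerun of the power calculation, with no added participants. The stated power will look less favourable.
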